Long-term follow-up of ACL-reconstruction using patellar tendon graft versus hamstring tendon graft

[name]
Date 2023-04-17

Protocol:

Participating parts

St. Olav's Hospital, Department of Orthopedics: [name], [name], [name].

Lovisenberg Diaconal Hospital, Department of Orthopedics: [name].

Haralds plass Deaconess Hospital, Department of Orthopedics: [name]

Haralds plass Deaconess Hospital, Department of Radiology: [name]

Norwegian University of Science and Technology, Faculty of medicine: [name], [name].

Introduction

Rupture of the anterior cruciate ligament (ACL) is a common soft-tissue knee injury, and has increased in number over the last twenty years [1, 2]. Reconstructing the ligament may be important for maintaining the stability and preventing further damaging of the knee [1]. The two most commonly used grafts in reconstructions are the autologous patellar tendon grafts and hamstring tendon grafts [3, 4].

There is yet to be a universally established agreement regarding which reconstruction method of an ACL is preferred [3-7]. The method using the central third of the patellar tendon with proximal and distal bone blocks as the replacement has been used since the late 80s and is well documented with good results [6, 8]. When the technique using the hamstring tendon grafts was introduced, its popularity increased [7, 9]. Arguments favoring each of the methods depend on which variables one values the most. In some studies, the patellar tendon group reported problems regarding anterior knee pain and decreased sensitivity of the knee, whereas for the hamstring tendon group there was reported increased weakness of the hamstring muscles and knee laxity [5, 6, 8]. However, the overall assessment and satisfaction in multiple short-term/semi-long studies have shown little to no difference [6, 8, 10].

The aim of this prospective randomized multicenter study is to compare the use of bone-patellar tendon-bone (BPTB) grafts and double-looped semitendinosus gracilis (DLSG) grafts for reconstruction of the anterior cruciate ligament, 17-20 years after the surgery. The null hypothesis is that there will be no significant differences at this long-term follow-up evaluation between the two methods.

Method and material of the first study

[name] et al. recruited 115 patients with rupture of the anterior cruciate ligament in the period of 2001-2004, and randomized them to either reconstruction with bone-patellar tendon-bone (BPTB) grafts fixed with metal interference screw graft, or double-looped semitendinosus gracilis (DLSG) grafts fixed with Bone Mulch Screws and WasherLoc Screws [6]. The surgeries were performed at four different hospitals.

After one and two years, the patients were examined by an independent observer, using a series of objective tests, as well as recording the patients' subjective opinion of their knee function. The subjective tests used were Tegner's activity score, Lysholm's functional score and Modified Cincinnati Score. The objective tests used were Lachmann's test, pivot shift and KT-1000, as well as Cybex and Biodex to measure muscle strength.

Inclusion and exclusion criteria from the original study, which also will be used for this study:
Criteria for inclusion:

Primary reconstructions of isolated ACL-ruptures. Surgery at least 6 weeks after injury. Age 18-45 years.

The patient must understand and accept the written consent. The written consent must be signed by the patient before surgery. Normal two-plane X-ray of the knee.

Criteria for exclusion:

>5mm + chronic MCL-injury in the same knee.

Patient with major additional injury in the knee: combined instability, cartilage injuries Outerbridge grade 3-4 and at least 1cm in diameter on the femoral condyle and major meniscal lesions with meniscal repairs.

Patients having problems following the protocol.

The patient does not understand the written consent or will not sign it.

Patients with a history of alcohol or drug abuse the last three years.

The patient has received any investigational drugs within 30 days prior to admittance to this study.

The patient has O.A., podagra, RA, Bechterew's disease or chondrocalcinosis.

The patient has malalignment with more than 5 degrees valgus and no varus compared to a normal knee.

The patient has patellofemoral instability.

The patient is obese with BMI>30.

The patient has a present or former serious illness that makes follow-up or rehabilitation of the patient difficult.

Former major surgical procedures in the same knee, including prosthesis.

Treated or untreated anterior cruciate ligament injury in the other knee.

Method and material

The present study is a long-term follow-up of a prospective randomized multicenter study.

The patient recorded outcome scores will be Tegner's activity score, Lysholms's functional score and the Knee injury Osteoarthritis Outcome Score (KOOS). The examinations include Lachmann's test, pivot shift and KT-1000. We also plan to include radiographs to evaluate the degree of arthrosis 17-20 years after the surgery, and Cybex or Biodex to examine the hamstring and quadriceps strength. The radiographic positioning will be knee AP weight-bearing standing bilateral and lateral view, as well as skyline projection. The Kellgren-Lawrence classification will be used to assess the degree of osteoarthritis.

Even though 115 patients were included in the original study, we will only attempt to contact 114 due to lost inclusion-papers between the 2-year and 7-year follow-up [8]. During the spring of 2022, the patients will receive an invite to participate in the follow-up study. Following this, we will call the patients to uncover different circumstances that might exclude certain patients from the clinical assessment. This includes revision of the reconstruction in question, total knee replacement or total knee arthroplasty, and if the knee had been injured beforehand. The clinical examination will be carried out by both a medical student and an experienced orthopedic surgeon. Hopefully all the patients will be examined over the course of two days at each location, and if needed, the rest will be examined at a later date. We will try to accommodate for the patients' needs as much as possible.

Hypothesis

Our hypothesis is that there will be no difference in the long-term outcome between the two groups. However, it will be interesting to see how many patients have received a prosthesis, and how many patients struggle with arthrosis. As the previous follow-up studies showed a significant difference in total flexion work between the two groups, we will be interested in detecting a persistent difference between the groups.

Another interesting aspect will be the rate of graft failure between the two groups. Other studies, such as Freedman et al., Wagner et al. and Samuelsen et al. have shown a lower rate of graft failure in the BPTB grafts compared to the DLSG grafts [11-13]. While Sajovic et al. showed the opposite; lower rate for the DLSG grafts compared to the BPTB grafts [10]. Our original study has yet to show any difference regarding this.

Feasibility

The strength of the study is the randomization and the long follow-up period of 17-20 years. The possible limitations are the fact that there may be a problem recruiting enough patients to the follow-up, and that we might not be able to get x-rays of the patients at the different hospitals, as this is a matter of cost and availability. In addition, the different hospitals may not have a Biodex available.

Publicity plan

The goal for the paper is to be published in an international journal and probably be presented at conferences. For article, that hopefully will be published in journals, [name] will stand as first author, and [name] and [name] as contributing authors. [name] will be listed last, as the main supervisor. The tentative order for the published article: [name], [name], [name], [name], [name], [name] and [name].

Economy

Our estimated expenses include flights to Bergen and Oslo, to collect the patient data. We assume we'll need two separate trips to each city, as some patients probably won't be able to meet us for the first round. Round trip Bergen x2 ~2500 kr. Round trip Oslo x2 ~2500 kr. To contact all the possible patients, we will send out letters before contacting them by phone. Estimated expense: 1000 kr.

Our intention is to include radiographs and Biodex as objective findings in the study.

Estimated expenses for Biodex: 70000kr. Estimated expenses for radiographs: 170000kr.

These are indicative prices from the companies we plan to buy the services from.

We have applied to the hospital for funding at a total of 240000kr, which has been granted.

From NTNU, our university, a total of 5000kr is granted for this project.

Ethics

The REK-application was submitted on the 24th of December 2021. Application number: 391796. Additionally, the project will be reported to NSD when the REK-application is approved.

References

1. Tiamklang, T., et al., *Double-bundle versus single-bundle reconstruction for anterior cruciate ligament rupture in adults*. Cochrane Database of Systematic Reviews, 2012(11).
2. LaBella, C.R., W. Hennrikus, and T.E. Hewett, *Anterior cruciate ligament injuries: diagnosis, treatment, and prevention*. Pediatrics, 2014. **133**(5): p. e1437-50.

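### The telephone screen can leave revised and replaced knees out of the clinical assessment, which limits the graft comparison to surviving knees; the re-used entry criteria also need a time point

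*Protocol*

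**What the plan says.** **Telephone screen (Method and material).** After the invitation letter, "we will call the patients to uncover different circumstances that might exclude certain patients from the clinical assessment". The circumstances named are revision of the study reconstruction, knee replacement, and an injury to the knee *beforehand*. The list is introduced as a set of inclusions, so it is open. The text does not say before what the injury must have happened, or whether the clinical assessment covers the radiographs as well as the physical examination.

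**Outcomes (Method and material; Hypothesis).** The follow-up covers laxity tests, muscle strength, patient-reported scores and radiographs. For the last, "The Kellgren-Lawrence classification will be used to assess the degree of osteoarthritis". The Hypothesis section adds an interest in how many patients have a prosthesis or arthrosis, and in graft failure by group.

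**Entry criteria (Method and material of the first study).** The list is introduced with "Inclusion and exclusion criteria from the original study, which also will be used for this study". It includes "Surgery at least 6 weeks after injury. Age 18-45 years" and a normal X-ray. It excludes a patient under "The patient has O.A., podagra, RA" and under "Former major surgical procedures in the same knee, including prosthesis". The introducing sentence gives no time at which the criteria apply.

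**The concern.** Revision and knee replacement happen after randomisation. They are poor results, and they may depend on which graft was used. The Hypothesis section itself cites studies in which graft failure differed by graft, some favouring one graft and one favouring the other. If these knees leave the clinical assessment in unequal numbers, the knees that remain are no longer compared as randomised, and the graft with more failures looks better than it was. The study's hypothesis is that the grafts do not differ, so a selection that can hide a difference matters. The Feasibility section also names randomisation as a strength of the study, and this screen can weaken it.

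The criteria sentence raises a smaller problem. Applied at follow-up, it would remove by definition patients with osteoarthritis or a prosthesis, whom the study wants to describe.

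**Working it through.** The protocol states no event count, sample size calculation or effect size for this point, so there is no figure to reproduce. The screen is examined by an illustration under stated assumptions, and the criteria sentence by comparing sections.

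**1. Laxity under the screen**

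Inputs:
- 114 patients to be contacted (Method and material).
- *Assumed:* an equal split, 114 / 2 = 57 per graft, with all patients taking part.
- *Assumed:* the same share *p* of abnormal laxity among examined knees of both grafts, from 10% to 30%.
- *Assumed:* one graft has 0, 3 or 6 more revised or replaced knees than the other.

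Let *r* be the share revised or replaced in a graft group. Examined knees alone give a difference of *p* − *p* = 0. If revised and replaced knees count as failures, the share with failure or abnormal laxity is *r* + (1 − *r*)*p*. The difference between grafts is therefore (1 − *p*) × (difference in *r*).

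| Excess knees | Difference in *r* | Hidden if *p* = 10% | Hidden if *p* = 30% |
|---|---|---|---|
| 0 | 0 | 0 | 0 |
| 3 | 3/57 = 5.3 points | 5.3 × 0.9 = 4.7 | 5.3 × 0.7 = 3.7 |
| 6 | 6/57 = 10.5 points | 10.5 × 0.9 = 9.5 | 10.5 × 0.7 = 7.4 |

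**2. Osteoarthritis, only if the screen also covers radiographs**

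*Assumed:* osteoarthritis in a share *q1* of revised or replaced knees and *q0* of the others, equal by graft. The difference among all knees is (difference in *r*) × (*q1* − *q0*), and it is 0 among examined knees.
- Revision or replacement 5% v 10%, *q1* = 80%, *q0* = 50%: 0.05 × 0.30 = 1.5 points.
- Revision or replacement 5% v 15%, *q1* = 100%, *q0* = 30%: 0.10 × 0.70 = 7 points.

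**3. The criteria sentence**

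- Age: 18 + 17 = 35 to 45 + 20 = 65 at follow-up. Since 45 − 17 = 28, anyone older than 28 at surgery is over 45 throughout the 17 to 20 year window. The age criterion cannot sensibly apply at follow-up.
- One criterion carries its own date: "The written consent must be signed by the patient before surgery".
- The list stands under the heading for the first study.
- Of the 115 original patients, "we will only attempt to contact 114 due to lost inclusion-papers between the 2-year and 7-year follow-up". Lost papers are the only reason given for the missing patient.

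All four point to status at original entry. The clash with the osteoarthritis and prosthesis outcomes arises only if the sentence is read as applying at follow-up.

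**The case against.** Several objections have force.

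- *The screen is bounded.* It says patients might be excluded, and from the clinical assessment, not from the study. The text then moves to the clinical examination, and radiographs are introduced separately, so the narrow reading is plausible. This stands as far as it goes. Even on the narrow reading, though, laxity and strength are compared only in surviving knees.
- *Prosthesis and graft-failure counts are already planned.* This stands. A reader might infer that the screen loses them, but the call asks about revision and replacement and can supply both. What the counts do not do is correct a laxity result that is read on its own.
- *Handling of such knees belongs in the analysis plan.* This stands in part. Analysis rules may well be in a plan not shown here. But the protocol states who may be left out of the assessment, and that rule is open to comment as it is written.
- *The size is assumed.* This stands. The split, the laxity shares and the imbalances come from no section, the range starts at zero, and the Hypothesis section says the original study has so far shown no difference in graft failure.
- *The criteria sentence is only wording.* This stands. A reader might infer that patients with osteoarthritis, a prosthesis or age over 45 were barred from follow-up. The document does not support that: the dated consent criterion, the age arithmetic and the plan to contact 114 of 115 patients all speak against it.

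**Conclusion.** The main point holds for the telephone screen. As written, it allows revised and replaced knees to be left out on account of events that follow randomisation and that are themselves of interest. The laxity and strength comparisons, and the osteoarthritis comparison if radiographs are covered, would then describe surviving knees only.

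The size cannot be known from the protocol. Under the assumptions in step 1, the amount hidden runs from nothing, with no imbalance, to 9.5 percentage points with six more failed knees in one graft. If radiographs are covered, the combinations in step 2 hide 1.5 to 7 points of osteoarthritis. These figures show what the rule could do. They are not evidence that a bias occurred or that it favours either graft.

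The criteria sentence is a minor wording conflict with a clear likely intent. The screen should be fixed, and the sentence needs only a clarification.

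**What to change.** In Method and material:
- State that all randomised patients who can be contacted and consent stay in the follow-up population, by randomised graft, and that the screen limits only the physical examination.
- Close the list of circumstances and say what *beforehand* refers to.
- Beside the laxity results, report by randomised graft a combined proportion: revised, replaced or abnormal laxity.
- In the osteoarthritis comparison, keep replaced knees as a separate worst category beside the Kellgren-Lawrence grades, and grade revised knees where radiographs are obtained.

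In Method and material of the first study, reconcile the criteria sentence with the outcomes by saying that the criteria were applied once, before the original surgery.

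The cost is a few sentences and a little more analysis, since the planned call already asks about revision and replacement. If the screen was meant to cover radiographs, a few more would be needed. The Economy section already budgets radiographs, although the Feasibility section warns that cost and availability may limit them.

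### Does the stated follow-up of 17-20 years conflict with recruitment in 2001-2004 and invitations in spring 2022?

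*Protocol*

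**What the plan says.** The follow-up time appears in three places, each time as 17-20 years:

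- the aim, in the Introduction: "for reconstruction of the anterior cruciate ligament, 17-20 years after the surgery";
- the radiographic plan, in Method and material: "evaluate the degree of arthrosis 17-20 years after the surgery";
- the strengths, in Feasibility: "the long follow-up period of 17-20 years".

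Two other statements fix the calendar. Method and material of the first study says that the original investigators "recruited 115 patients with rupture of the anterior cruciate ligament in the period of 2001-2004". Method and material says: "During the spring of 2022, the patients will receive an invite to participate in the follow-up study". Telephone calls and examinations come after that, and "if needed, the rest will be examined at a later date". The protocol gives no month for the first or last operation, no closing date for visits and no rule for rounding years.

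**The concern.** The figure looks like a leftover from a schedule with examinations in 2021, since that is the only calendar year from which simple subtraction returns both 17 and 20. Yet the Ethics section dates the ethics application 24 December 2021, and invitations come only in the following spring. Any operation done in 2001 would then be more than 20.0 years old at invitation, and older still at a later visit.

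Two things could be at stake. If 17-20 years were a window, the earliest-operated patients might fall outside it. If it is a description, it could misstate the time point for osteoarthritis, knee prosthesis and graft failure, all of which accumulate with time. The interval is also part of the aim and is put forward as a strength of the study.

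**Working it through.** **Inputs.** Recruitment 2001-2004 (Method and material of the first study). Invitations in spring 2022 (Method and material), taken here as 1 March to 31 May 2022, which is an assumption. The outer limits treat the recruitment years as surgery years: earliest operation 1 January 2001, latest 31 December 2004.

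**1. Calendar-year subtraction.**

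- 2021: 2021 − 2004 = 17 and 2021 − 2001 = 20. This reproduces the stated range.
- 2022: 2022 − 2004 = 18 and 2022 − 2001 = 21.

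**2. Exact dates.** Years = (visit date − surgery date in days) / 365.25.

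| Visit date | Surgery 31 Dec 2004 | Surgery 31 Dec 2001 | Surgery 1 Jul 2001 | Surgery 1 Jan 2001 |
|---|---|---|---|---|
| 1 Mar 2022 | 17.16 | 20.16 | 20.67 | 21.16 |
| 31 May 2022 | 17.41 | 20.41 | 20.91 | 21.41 |
| 31 Dec 2022 | 18.00 | 21.00 | 21.50 | 22.00 |

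The lower limit of 17 fits spring 2022. The upper limit, read as exactly 20.0, is exceeded by every 2001 operation, by at most 21.41 − 20 = 1.41 years in spring 2022 and 22.00 − 20 = 2.00 years at the end of 2022.

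**3. Completed years.** Follow-up of 17 to 20 completed years runs from 17.0 to just under 21.0, which is four years wide. That is enough for a recruitment period of up to four years. For a visit on 31 May 2022, every operation after 31 May 2001 has fewer than 21 completed years. The stated range is then right for spring 2022 visits if the first operation came after spring 2001.

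**4. How many patients could lie outside the label.** Assume even accrual over four full years, which the protocol does not state. The share beyond a cut c is (longest follow-up − c) / 4.

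| Visit date | Cut at 20.0 years | Cut at 21.0 years (20 completed) |
|---|---|---|
| 1 Mar 2022 | (21.16 − 20)/4 = 29% | (21.16 − 21)/4 = 4% |
| 31 May 2022 | (21.41 − 20)/4 = 35% | (21.41 − 21)/4 = 10% |
| 31 Dec 2022 | (22.00 − 20)/4 = 50% | (22.00 − 21)/4 = 25% |

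The apparent size of the problem depends mainly on the rounding convention.

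**5. What the figure drives.** None of the inclusion and exclusion criteria uses time since surgery. Neither do the circumstances to be checked by telephone, which are revision, knee replacement and earlier injury. The protocol ties no sample size or test to the range.

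**The case for a change.** The strongest case for a correction is that the completed-years reading is a rescue that the protocol does not state, and that it weakens as visits move later. At the end of 2022 every 2001 operation is 21.0 to 22.0 years old, so 17-20 would then hold only if nobody was operated on in 2001. Late visits are foreseen: the Economy section budgets two trips each to Bergen and Oslo because some patients are expected to miss the first round. The protocol is dated 17 April 2023, when the outer limits would be 18.3 to 22.3 years. The correction would be one figure in three places.

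Part of this stands. The upper limit is not guaranteed, and with no closing date the range could be one to two years short at the top.

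The rest does not carry. The document date is not a visit date: the text still treats the spring 2022 invitations as future and schedules nothing in 2023. The years given are for recruitment, and consent had to be signed before surgery, so operations may have come somewhat later, which lowers the upper end. A replacement of 18-21 years would be no safer, because a late-2004 operation seen in spring 2022 is only 17.2 to 17.4 years old. A statement that nobody is excluded for time since surgery would answer a rule that does not exist.

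**Conclusion.** No change to the plan follows. The 20-year upper limit is not secured by the stated dates, but a contradiction is not proven. If operations spanned all of 2001-2004 and visits took place in spring 2022, about 17-21 years would be the better label; if visits ran to the end of 2022, the range could reach 22 years. In completed years the stated range is correct for spring 2022 visits, provided that the first operation came after spring 2001.

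Even in the less favourable case this is a clerical matter. The label does not change the true time since surgery of any patient, nor who is eligible or what is compared. Patients were randomised between the grafts over the same recruitment period, so a range that is short at its upper end does not favour either graft. The time point that readers need for osteoarthritis and graft failure can be taken from the actual surgery and examination dates when the results are reported. This assumes that those dates are on file, which the protocol does not say, but which a follow-up of this cohort can hardly do without. Rewording the range now would give no gain in the analysis.

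### The telephone screen can withhold the examination for an undefined earlier knee injury, most naturally a re-injury after randomisation, so the examined knees may be selected by graft

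*Protocol*

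**What the plan says.** The Protocol's Method and material section describes a call made after the invitation letter: "we will call the patients to uncover different circumstances that might exclude certain patients from the clinical assessment". The circumstances follow in one list: "This includes revision of the reconstruction in question, total knee replacement or total knee arthroplasty", "and if the knee had been injured beforehand". The list does not say before what the injury must have occurred, or what kind or severity of injury counts.

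The same section describes what the examination contains: "The examinations include Lachmann's test, pivot shift and KT-1000". Strength testing and radiographs are planned in addition. The Hypothesis section adds: "Another interesting aspect will be the rate of graft failure between the two groups". The Protocol does not define graft failure or say whether it is counted from the call, from records or from the examination.

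Two places under Method and material of the first study bear on the meaning of the item. The entry criteria begin "Primary reconstructions of isolated ACL-ruptures. Surgery at least 6 weeks after injury", so every patient had an injured knee before the index operation. The criteria are introduced as "Inclusion and exclusion criteria from the original study, which also will be used for this study".

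**The concern.** A rule on who is examined belongs in the protocol, and this one cannot be applied uniformly. Two callers who understand the time point differently would screen out different patients.

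The larger matter is what happens under the most natural meaning. A new injury to the operated knee is one way in which a graft rupture comes about. Leaving such knees out of the examination means that Lachman, pivot shift, KT-1000 and, if done at the same visit, strength are compared on knees chosen by something that happened after randomisation. That event may depend on the graft. The Hypothesis section cites studies in which graft failure differs between the two grafts, in both directions, and the Introduction mentions reports of more laxity with hamstring grafts. Randomisation is the strength that the Feasibility section claims, and selection of this kind weakens it.

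A revised graft would be learned of in the call. A rupture that was never revised, and that the patient may not know of, is most likely to be found by the laxity tests, which the item can withhold.

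**Working it through.** The Protocol states no failure rate, re-injury rate, sample size calculation or alpha, so there is no figure to reproduce. The check is mainly one of reading, followed by an illustration.

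**Step 1. What the item can mean.**

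- *Any injury before the index operation.* The entry criteria require an ACL rupture and at least 6 weeks from injury to surgery. The item is then true of all 114 patients to be contacted and cannot be what is meant.
- *Some other injury before the index rupture.* This fits the carried-over criteria, which require an isolated rupture and exclude major additional injury and former major surgery in the knee. It is not true of everyone and removes no re-injured knees. But eligibility was settled at entry in 2001-2004. Applying it again by telephone would drop randomised patients on recall about two decades old.
- *An injury before the follow-up visit.* The two companion items, revision and replacement, are events after the index operation. In that list, this is the most natural reading. It makes the item an exclusion after randomisation.

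**Step 2. When failures would be missed.** Three things must hold together: the third reading applies, callers act on a circumstance that only *might* exclude, and failure is counted only in examined knees. The Protocol settles none of the three.

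**Step 3. Illustration for graft failure.** Assumptions, none from the documents: true failure 10% in one arm and 18% in the other, and a share u of an arm's graft failures that is unrevised and lost through the screen.

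- Observed rate if screened-out patients stay in the denominator: f(1 − u).
- Observed rate if lost failures also leave the denominator: f(1 − u)/(1 − fu).

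| u in 10% arm | u in 18% arm | Observed rates (kept in denominator) | Difference, points | Difference if also removed from denominator |
|---|---|---|---|---|
| 0 | 0 | 10.0% v 18.0% | 8.0 | 8.0 |
| 20% | 20% | 8.0% v 14.4% | 6.4 | 6.8 |
| 50% | 50% | 5.0% v 9.0% | 4.0 | 4.6 |
| 60% | 60% | 4.0% v 7.2% | 3.2 | 3.8 |
| 60% | 20% | 4.0% v 14.4% | 10.4 | 14.9 − 4.3 = 10.7 (before rounding) |
| 20% | 60% | 8.0% v 7.2% | −0.8 | 8.1 − 8.2 = −0.1 |

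With equal shares the difference shrinks. With unequal shares it can grow beyond the true 8 points or vanish. At u = 0 nothing is lost; this is the case if ruptures are all learned of in the call and counted.

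**Step 4. Illustration for laxity.** Assume 57 patients per arm (114/2, equal arms and full attendance). If 3 of them have 6 mm more KT-1000 laxity than the mean of the others, leaving them out lowers that arm's mean by 6 × 3/57 = 0.32 mm. The 3 and the 6 mm are also assumed.

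**The case against.** The strongest case against is that this is loose wording and no more. The call is meant to uncover circumstances, so a re-injury, or a rupture already diagnosed, would be reported there. The screen concerns the clinical assessment only; the Protocol does not say that these patients leave the study, the patient-reported scores or the failure count. How failure is ascertained may stand in an analysis plan that is not at hand. Graft failure is named as an aspect of interest and not as a primary outcome. Even with nobody excluded, 10% v 18% with 57 per arm would have only about 24% power: z = 0.08/√((0.10×0.90 + 0.18×0.82)/57) = 1.24 against 1.96, two-sided 5%.

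Much of this stands. A reader might infer that the item must either cover every patient or remove re-injured knees; the reading of an injury before the index rupture shows that these are not the only choices. A reader might also infer that failures will be undercounted and that the bias runs towards no difference. The text supports only that they could be missed, and the last two rows of the table show that the direction depends on shares nobody knows.

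Two things do not fall away. A failure count completed by telephone would not repair the laxity and strength comparisons, which would still rest on selected knees. And the word *might* leaves an undefined rule to the caller's discretion, which is no safeguard. It is also fair to say that revision and replacement stay on the same list and select the examined knees in a similar way; changing the injury item does not remove that.

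**Conclusion.** The item is badly fixed: it has no time point and no injury type. On its most natural reading it is an exclusion after randomisation that may depend on the graft, and it can bias the laxity and strength comparisons. Missed unrevised ruptures are a risk under that reading, conditional on failure being counted only in examined knees. On the reading of an injury before the index rupture, it loses randomised patients for no gain. No reading gives a reason to keep it.

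The size cannot be established from the documents. The figures above rest on assumed rates, shares and attendance. They show only that an effect of several percentage points in either direction is arithmetically possible. The conclusion on wording and selection does not depend on them. This is a cheap improvement, not a flaw that invalidates the study.

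**What to change.** - Remove knee injury from the reasons for withholding the examination.
- In the same call, record any injury to the operated knee since the index operation: date, type and treatment.
- Invite these patients to the planned examination like all others.
- Count known graft ruptures, revised or not, as graft failure in the randomised arm, and state that patients who are not examined stay in the failure count.
- If a result in knees without re-injury is wanted, report it as a labelled secondary description.

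Invitations were planned for spring 2022 and the Protocol is dated April 2023, so the calls may be complete. In that case, state how the item was applied, report the numbers screened out by arm, keep those patients in the failure count, and offer them the examination where feasible.

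The cost is one sentence in the Protocol, a line on the telephone form and a few more visits, which are extra visits if the examination days have passed. Laxity and strength results will be somewhat more variable because re-injured knees stay in.
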